- Treatment with prior anti-PD-1/anti-PD-L1/2 antibodies is not allowed.

Cohort D

- Histological or cytological evidence of recurrent advanced and/or metastatic **gastric or gastroesophageal junction adenocarcinoma** whose tumors express PD-L1 (CPS >1%), with disease progression on or after 2 or more prior lines of therapy including fluoropyrimidine- and platinum-containing chemotherapy and if appropriate, HER2/neu-targeted therapy.
- Subjects without prior anti-PD-1/anti-PD-L1/2 antibody treatment are eligible.
- Subjects who have received prior anti-PD-1/anti-PD-L1/2 antibodies are eligible provided (i) they have had documented best observed response (BOR) of SD or better in response to an anti-PD1/PD-L1/2 therapy, AND (ii) ≥6 weeks interval since their last dose of prior anti-PD-1/anti-PD-L1/2 treatment

Cohort E

- Histological or cytological evidence of unresectable or metastatic **TMB-H** and **MSS** solid tumors (TMB as defined by an FDA-approved test, e.g., Foundation Medicine >10 mutations/megabase or a Laboratory Developed Test approved by the sponsor (e.g., Guardant Health), that have progressed following prior treatment and who have no satisfactory alternative treatment options. Subjects without prior treatment with anti-PD-1/anti-PD-L1/2 antibody treatment are eligible. Subjects who have received prior anti-PD-1/PD-L1/2 treatment are eligible with at least 6 weeks since their last dose of these prior treatments. Subjects must have had a previous SD or better in response to an anti-PD1/PDL-1/2 therapy. Subjects with the following TMB-H and MSS solid tumors will enroll into the tumor specific cohorts noted below after discussion with the sponsor:

Cohort A: Endometrial cancer PD-1/PD-L1/2 naïve

Cohort C: Cervical carcinoma

Cohort F: Rare tumors (sarcoma, uveal melanoma, germ cell carcinoma)

Cohort H: Ovarian cancer

Cohort F

Rare Tumors

1. Germ Cell Tumors

- Histologically or cytologically confirmed seminoma or non-seminoma testicular **germ cell tumors**.
- Recurrent, advanced and/or metastatic disease, including new lesions, persistently elevated β - human chorionic gonadotropin (HCG) or alpha 1-fetoprotein (AFP) or increase in consecutive elevated serum tumor markers (β -HCG or AFP) done at least one week apart after prior high-dose chemotherapy (HDCT).

Subjects deemed not to be candidates for benefit from potentially curative HDCT may also be eligible including those with:

- (i) inadequate renal function for HDCT

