6. STUDY DESIGN

6.1. Summary of Study Design

This is an open-label, multicenter, Phase 1b/2 basket study designed to evaluate the efficacy, safety, tolerability, pharmacokinetics (PK), and pharmacodynamics (PD) of etigilimab in combination with nivolumab in subjects with recurrent, locally advanced and/or metastatic solid tumors who are not candidates for available, curative standard of care therapies. In cohorts enrolling tumor types for whom anti-PD-1 antibody therapy is approved treatment for recurrent, locally advanced or metastatic disease, subjects may be enrolled prior to treatment with anti-PD-1 antibody therapy.

Subjects will be assigned to receive etigilimab (█ mg every 2 weeks for subjects ≥ 50 kg, █ mg/kg dose every 2 weeks for subjects < 50 kg) in combination with nivolumab (240 mg every 2 weeks) and will continue until protocol-defined discontinuation criteria are met (refer to Section 7 of the protocol). Additional doses and schedules may also be evaluated. This study will evaluate both subjects who have not previously been treated with immune checkpoint inhibitors (CPI) as well as those who have received prior CPI therapy and will include tumor types chosen for higher prevalence of TIGIT, and in select cohorts, subjects with high PD-L1 expressing tumors as measured by immunohistochemistry (IHC). Tumor types selected for this study include recurrent, locally advanced and/or metastatic endometrial carcinoma (EC), cervical cancer (CC), gastric cancer and gastro-esophageal junction carcinoma (GC), squamous cell carcinoma of the head and neck (HNSCC), ovarian cancer (OC), rare cancers (metastatic testicular germ cell tumor, uveal melanoma and sarcoma) and any subject with concomitant tumor mutation burden high (TMB-high) and microsatellite stable (MSS) tumors. As TIGIT has been implicated in PD-L1 resistance, subjects who have received or progressed following a CPI (post-CPI subjects) will also be enrolled in select tumors including EC, HNSCC and TMB-high/MSS tumors. Parallel cohorts of up to 20 subjects per cohort will be evaluated.

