6.3. Interim Analysis

There is no formal interim analysis planned for this study, although interim futility monitoring was to be carried out using a Simon Two-Stage design for each individual cohort, when up to 10 subjects had sufficient data (either discontinued study drug treatment or have at least one post-baseline imaging assessment) for Objective Response Rate (ORR) and Duration of Response (DoR) evaluation by RECIST v1.1. This evaluation occurred for both of the cervical and uveal cohorts (cohorts C and F) and approval was given to proceed, the evaluation was not required for the other cohorts before the study was terminated.

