For either CR or PR to be ‘confirmed’ the same overall response needs to be achieved at the subsequent visit, which should be at least 4 weeks later. The best overall response (BOR) is then the best response achieved in order of CR, PR, SD, PD, NE, where a subject cannot be defined as having BOR of CR, PR or SD if they have previously experienced PD.

Response is recorded for each participant at each tumor response visit using the criteria outlined above. The response recorded in the database will be used to evaluate the objective response rate and all other endpoints related to the response based on RECIST v1.1 guidelines.

Objective Response Rate (ORR) is then defined as the proportion of subjects who achieve a best overall response of Confirmed CR or Confirmed PR. Subjects with not-evaluable response (NE) are counted as non-responders.

The number and percentage of subjects who have achieved objective response will be summarised, by cohort, including sub-cohort, along with the 95% Clopper-Pearson CI.

Additionally the number and percentage of subjects with CR and PR (confirmed and unconfirmed), SD, PD and NE will be summarised by cohort, including sub-cohort.

A swimmer plot, displaying the response for each subject over their time in the study, will be presented for all subjects as well as for gynaecological cohorts (Cohort A, E and H) and rare tumor sub-cohorts (Cohort F) with a line per subject and each response/important event highlighted on the line as appropriate.

A waterfall plot will also display the percentage reduction in overall sum of diameters over the time in study for each subject. This will again be presented for all subjects and for gynaecological cohorts

(Cohort A, E and H) and rare tumor sub-cohorts (Cohort F). Additionally a spider plot will be produced for each set of cohorts, which will display the percentage change from baseline in sum of the longest diameter over time, where the lines will be displayed by best overall response.

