13.3. List of Figures

Figure Number	Figure Title
14.1.1	Swimmer Plot of Study Progression – Response-Evaluable Analysis Set
14.1.2	Swimmer Plot of Study Progression – Gynaecological Indications – Response-Evaluable Analysis Set
14.1.3	Swimmer Plot of Study Progression – Rare Tumors – Response-Evaluable Analysis Set
14.2.1.1	Waterfall Plot of Percentage Change from Baseline in the Sum of Diameters – Response-Evaluable Analysis Set
14.2.1.2	Waterfall Plot of Percentage Change from Baseline in the Sum of Diameters – Gynaecological Indications – Response-Evaluable Analysis Set
14.2.1.3	Waterfall Plot of Percentage Change from Baseline in the Sum of Diameters – Rare Tumors – Response-Evaluable Analysis Set
14.2.2.1	Spider Plot of Percentage Change from Baseline in the Sum of Diameters Over Time – Response-Evaluable Analysis Set
14.2.2.1	Spider Plot of Percentage Change from Baseline in the Sum of Diameters Over Time – Gynaecological Indications – Response-Evaluable Analysis Set
14.2.2.1	Spider Plot of Percentage Change from Baseline in the Sum of Diameters Over Time – Rare Tumors – Response-Evaluable Analysis Set
14.2.3.1	Kaplan-Meier Plot of Duration of Response – Response-Evaluable Analysis Set
14.2.3.2	Kaplan-Meier Plot of Duration of Stable Disease – Response-Evaluable Analysis Set
14.2.3.3	Kaplan-Meier Plot of Duration of Response (iRECIST) – Response-Evaluable Analysis Set
14.2.3.4	Kaplan-Meier Plot of Progression Free Survival – Response-Evaluable Analysis Set
14.2.3.5	Kaplan-Meier Plot of Progression Free Survival (iRECIST) – Response-Evaluable Analysis Set
14.2.3.6	Kaplan-Meier Plot of Overall Survival – Response-Evaluable Analysis Set

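### The gynaecological swimmer, waterfall and spider plots are specified as Cohorts A, E and H, which includes the biomarker-defined TMB-H/MSS cohort and leaves out cervical (C) and post-CPI endometrial (G)

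*SAP*

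**What the plan says.** SAP 10.8.1.1 asks for a swimmer plot of all subjects, and for further ones for "gynaecological cohorts (Cohort A, E and H") and for the rare tumour sub-cohorts. The waterfall plot follows with the same list, and the spider plot inherits it: "Cohort A, E and H) and rare tumor sub-cohorts (Cohort F). Additionally a spider plot will be produced for each set of cohorts".

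SAP 10.1.2 fixes the cohort labels: A is CPI-naive endometrial, C cervical, E TMB-H/MSS, G post-CPI endometrial and H ovarian.

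SAP 6.1 describes the TMB-H/MSS population as "any subject with concomitant tumor mutation burden high (TMB-high) and microsatellite stable (MSS) tumors". Protocol 3.1, under Cohort E, adds a carve-out: "Subjects with the following TMB-H and MSS solid tumors will enroll into the tumor specific cohorts noted below after discussion with the sponsor". The destinations named there are A (CPI-naive endometrial), C (cervical), F (rare tumours) and H (ovarian).

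The list of figures in SAP 13.3 gives titles only, for example "Swimmer Plot of Study Progression – Gynaecological Indications – Response-Evaluable Analysis Set", and names no cohorts. SAP Section 11, on changes to the protocol-specified analysis, does not mention the grouping.

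**The concern.** The title of a figure and the rule that selects its subjects should describe the same people, and here they do not. The list contains a cohort that is open to solid tumours of any site and from which most gynaecological cases are routed away. It lacks two cohorts whose tumour type is gynaecological by definition.

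SAP 10.1.3 states that no formal hypothesis testing will be done, so readers will look to the subject-level plots for a picture of activity. A gynaecological figure without cervical and post-CPI endometrial subjects would give an incomplete picture, and the Cohort E subjects in it may have other tumours. Because the same list is written twice, a programmer following the SAP would build the figures on it, and a check of the output against the SAP would pass them.

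**Working it through.** No sample size, error rate or event count bears on this point. The check compares the listed cohorts with the cohort definitions.

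| Cohort | Label (SAP 10.1.2) | Defined by a gynaecological tumour? | In the 10.8.1.1 list? |
|---|---|---|---|
| A | Endometrial, CPI-naive | Yes | Yes |
| C | Cervical | Yes | No |
| E | TMB-H/MSS | No (biomarker) | Yes |
| G | Endometrial, post-CPI | Yes | No |
| H | Ovarian | Yes | Yes |

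1. Listed set = {A, E, H}. Set implied by the labels = {A, C, G, H}.
2. In both: {A, H}, which is 2 of the 4 gynaecological cohorts.
3. Omitted: {C, G}, the other 2 of 4.
4. Listed without being defined by a gynaecological tumour: {E}, 1 of the 3 listed.

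**Could E be meant as gynaecological?** The protocol sends TMB-H/MSS tumours that are CPI-naive endometrial, cervical or ovarian to A, C and H. The carve-out therefore removes from E most of the cases that would justify its place in the plot.

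**Could C and G be left out for lack of evaluable subjects?** No. The shell for Table 14.2.1, on the response-evaluable set, explains the absence of D (nobody recruited) and B (nobody response-evaluable), and keeps columns for C and G. The figures use the same analysis set.

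**Does anything else in the SAP group these cohorts?** The Kaplan-Meier shell, Table 14.2.2.2, sets out A, C, G and H side by side and leaves E to a repeat of the table with the Cohort F sub-cohorts. The shell does not call that layout gynaecological, so it is consistent with the implied set without defining it.

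**Which figures are affected?** Three: 14.1.2 (swimmer), 14.2.1.2 (waterfall) and the gynaecological spider plot. All three spider plots are numbered 14.2.2.1 in SAP 13.3, so that one has to be identified by its title.

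**The case against.** The strongest objection is to the remedy. No section states that the gynaecological set is A, C, G and H. The written list is one letter away from A, C and H. Those three are the gynaecological destinations in the Cohort E routing list and, with F, the cohorts from which the protocol excludes prior anti-PD-1/PD-L1 treatment. On that reading the error is a single wrong letter and G was left out deliberately as the post-CPI cohort. Only C would then be missing: 1 of 3 cohorts, not 2 of 4. This stands as a possibility. The figure title covers gynaecological indications without regard to prior treatment, which favours including G but does not settle it. Both readings agree that E is wrong and C is missing.

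The second objection is to the impact, and it largely stands. The primary objective evaluates each cohort independently. ORR and DCR are tabulated by cohort with exact intervals, and duration of response, duration of stable disease, PFS and OS are also reported by cohort. C and G remain in the all-subject swimmer, waterfall and spider plots. The grouped figures are supplementary displays.

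A reader might go further in three ways that the documents do not support:

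- **That the figures show the wrong patients altogether.** A and H are correctly included. The composition is wrong, not every subject in it.
- **That E necessarily brings in unrelated tumours.** The make-up of E is not given. G is not on the routing list and E accepts subjects with prior CPI treatment, so E may hold some post-CPI endometrial cases. The baseline shell has rows for salivary gland and mesothelioma, but a shell row does not show that anyone was enrolled.
- **That the plots drop a cohort shown to have met its stage 1 response threshold.** SAP 6.3 says: "This evaluation occurred for both of the cervical and uveal cohorts (cohorts C and F) and approval was given to proceed". Stopping at stage 1 is discretionary under protocol 9.1, so approval to proceed does not show that the threshold was met.

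**Conclusion.** The cohort list in SAP 10.8.1.1 is wrong as written. It conflicts with the SAP's own labels and with the figure titles, and nothing elsewhere in the SAP corrects or explains it. Three figures are affected. On the labels, each would include one cohort not defined by a gynaecological tumour and omit two that are. If G was left out on purpose, one is omitted. No estimate, interval or planned decision changes.

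The conclusion assumes that gynaecological has its ordinary meaning (endometrial, cervical, ovarian) and that the figures will be programmed from the text of 10.8.1.1. How many subjects would be misplaced cannot be worked out from the documents, because they give neither the cohort sizes nor the tumour types within E.

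**What to change.** In both places in SAP 10.8.1.1, replace the list with the cohorts defined by a gynaecological tumour, which by the labels are A, C, G and H. Apply that filter to Figures 14.1.2 and 14.2.1.2 and to the gynaecological spider plot.

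If the sponsor intends to leave out G as the post-CPI cohort, say so in the figure title or a footnote. If any gynaecological cases within E are wanted, add them by primary tumour location and state the rule. In every case remove E as a whole cohort and add C.

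The cost is one wording change made twice and one programming filter. If the SAP can no longer be amended, describe the departure in the clinical study report, as SAP Section 4 provides.

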10.8.2. Secondary Endpoints

10.8.2.1. Disease Control Rate

Disease control rate (DCR) is defined as the proportion of subjects who have achieved CR, PR, and SD. The number and percentage of subjects who have achieved disease control will be summarised, by cohort, including sub-cohort, along with the 95% Clopper-Pearson CI.

10.8.2.2. Duration of Response

Duration of response (DoR) is defined as the time, in days, from the first of the 2 assessments required for confirmed PR or CR to the time of the PD or death due to underlying cancer.

The duration will be calculated (in days) as:

Date of first overall response of PD or date of death due to underlying cancer (whichever is first) – Date of first of the two assessments required for confirmed CR or PR.

The duration of response will be summarised by cohort using descriptive summaries, which will not account for censoring. Additionally, Kaplan-Meier curves will be produced for each cohort along with a table summarising the median and 25th and 75th percentiles of the duration of response, inclusive of censoring, for each cohort, including sub-cohort.

[Kaplan-Meier plot: y-axis = cumulative proportion of participants who still have response, x-axis = day, one line for each cohort, including sub-cohort, overlayed on the same plot].

Exclusion

If a subject does not achieve confirmed CR or PR they will be excluded from this analysis.

Censoring

If a subject does not experience PD or death due to underlying cancer their duration will be censored at the date of their last disease assessment.

If a subject dies due to a cause other than underlying cancer they will be censored at the date of death.

If a subject does not have a disease assessment after their assessment confirming their response as CR or PR they will be censored at the date of their last disease assessment.

If a subject initiates another cancer treatment prior to PD/death their duration of response will be censored at the last assessment prior to initiation of the alternative cancer treatment.

If a subject experiences PD or death immediately following 2 or more visits at which their response was missing or NE their duration of response will be censored at the time of their last assessment prior to missing/NE response.

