Overall survival, PFS, and DoR will be summarized for each group using Kaplan-Meier methodology. Censoring rules will be detailed in the statistical analysis plan.

- For analysis of OS, all subjects will be followed for survival for up to 2 years, until withdrawal of consent, loss to follow up, or death, whichever occurs first. At the time of analysis of OS, any subjects who remain alive will be censored at the last date they were known to be alive.
- PFS is the time from the start of study treatment to the first evaluation showing PD or death, whichever occurs first. Subjects who do not experience PD or death will be censored per the censoring rules in the statistical analysis plan.

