10.8.2.3. Duration of Stable Disease

Duration of stable disease (DoSD) is defined as the time, in days, from the first date of treatment until the first date at which PD is experienced or the subject dies due to underlying cancer.

The duration will be calculated (in days) as:

Date of first overall response of PD or date of death from underlying cancer (whichever is first)
– Date of first treatment.

The duration of stable disease will be summarised by cohort using descriptive summaries, which will not account for censoring. Additionally, Kaplan-Meier curves will be produced for each cohort along with a table summarising the median and 25th and 75th percentiles of the duration of stable disease, inclusive of censoring, for each cohort, including sub-cohort.

[Kaplan-Meier plot: y-axis = cumulative proportion of participants who still have stable disease, x-axis = day, one line for each cohort, including sub-cohort, overlayed on the same plot].

Censoring

If a subject does not experience PD or death due to underlying cancer their duration will be censored at the date of their last disease assessment.

If a subject dies due to a cause other than underlying cancer they will be censored at the date of death.

If a subject does not have a disease assessment after their first treatment they will be censored at the date of their first treatment.

If a subject initiates another cancer treatment prior to PD/death their duration of stable disease will be censored at the last assessment prior to initiation of the alternative cancer treatment.

If a subject experiences PD or death immediately following 2 or more visits at which their response was missing or NE their duration of stable disease will be censored at the time of their last assessment prior to missing/NE response.

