Progression-free survival will be summarised by cohort, and sub-cohort for cohort F, using descriptive summaries, which will not account for censoring. Additionally, Kaplan-Meier curves will be produced for each cohort, and sub-cohort for cohort F, along with a table summarising the median and 25th and 75th percentiles of the progression-free survival, inclusive of censoring, for each cohort, including sub-cohort.

[Kaplan-Meier plot: y-axis = cumulative proportion of participants who are progression free, x-axis = day, one line for each cohort, including sub-cohort, overlayed on the same plot].

Censoring

If a subject does not experience PD or death they will be censored at the date of their last disease assessment.

If a subject does not have a disease assessment after their first treatment they will be censored at the date of their first treatment.

If a subject initiates another cancer treatment prior to PD/death they will be censored at the last assessment prior to initiation of the alternative cancer treatment.

If a subject experiences PD or death immediately following 2 or more visits at which their response was missing or NE they will be censored at the time of their last assessment prior to missing/NE response.

10.8.3.4. *Progression Free Survival (iRECIST)*

Progression-free survival (iPFS) is defined as the time, in days, from the first date of treatment until the first date at which iCPD is experienced or the subject dies due to any cause. Only deaths that occur within 30 days of the last tumor assessment will be included.

The duration will be calculated (in days) as:

Date of first overall response of iCPD or date of death due to any cause (whichever is first) – Date of first treatment.

Progression-free survival will be summarised by cohort, and sub-cohort for cohort F, using descriptive summaries, which will not account for censoring. Additionally, Kaplan-Meier curves will be produced for each cohort, and sub-cohort for cohort F, along with a table summarising the median and 25th and 75th percentiles of the progression-free survival, inclusive of censoring, for each cohort, including sub-cohort.

[Kaplan-Meier plot: y-axis = cumulative proportion of participants who are progression free, x-axis = day, one line for each cohort, including sub-cohort, overlayed on the same plot].

Censoring

If a subject does not experience iCPD or death they will be censored at the date of their last disease assessment.

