If a subject does not have a disease assessment after their first treatment they will be censored at the date of their first treatment.

If a subject initiates another cancer treatment prior to iCPD/death they will be censored at the last assessment prior to initiation of the alternative cancer treatment.

If a subject experiences iCPD or death immediately following 2 or more visits at which their response was missing or NE they will be censored at the time of their last assessment prior to missing/NE response.

10.8.3.5. *Overall Survival*

Overall survival (OS) is defined as the time from the first dose of study drug to death due to any cause.

For analysis of OS, all subjects will be followed for survival for up to 2 years, until withdrawal of consent, loss to follow up, or death, whichever occurs first. At the time of analysis of OS, any subjects who remain alive will be censored at the last date they were known to be alive.

The duration will be calculated (in days) as:

Date of death due to any cause – Date of first treatment.

Overall Survival will be summarised by cohort, and sub-cohort for cohort F, using descriptive summaries, which will not account for censoring. Additionally, Kaplan-Meier curves will be produced for each cohort, and sub-cohort for cohort F, along with a table summarising the median and 25th and 75th percentiles of the overall survival, inclusive of censoring, for each cohort, including sub-cohort.

[Kaplan-Meier plot: y-axis = cumulative proportion of participants who are alive, x-axis = day, one line for each cohort, including sub-cohort, overlayed on the same plot].

Censoring

If a subject is still alive at the end of follow-up they will be censored at the date they were last known to be alive.

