13.2. List of Tables

Table Number	Table Title
14.1.1	Participant Disposition – All Subjects
14.1.2.1	Demography – Safety Analysis Set
14.1.2.2	Demography of Cohort F – Safety Analysis Set
14.1.3.1	Baseline Disease Characteristics – Safety Analysis Set
14.1.3.2	Baseline Disease Characteristics of Cohort F – Safety Analysis Set
14.1.4.1	Prior Cancer Treatments – Safety Analysis Set
14.1.4.2	Other Prior Medications – Safety Analysis Set
14.1.4.3	Concomitant Medications – Safety Analysis Set
14.1.5	Investigational Product Exposure – Safety Analysis Set
14.2.1	Response – (RECIST v1.1) – Response Evaluable Analysis Set
14.2.2.1	Duration of Response (RECIST v1.1) – Response Evaluable Analysis Set
14.2.2.2	Duration of Response (RECIST v1.1) – KM – Response Evaluable Analysis Set
14.2.3.1	Duration of Stable Disease (RECIST v1.1) – Response Evaluable Analysis Set
14.2.3.2	Duration of Stable Disease (RECIST v1.1) – KM – Response Evaluable Analysis Set
14.2.4	Response – (iRECIST) – Response Evaluable Analysis Set
14.2.5.1	Duration of Response (iRECIST) – Response Evaluable Analysis Set
14.2.5.2	Duration of Response (iRECIST) – KM – Response Evaluable Analysis Set
14.2.6.1	Duration of Stable Disease (iRECIST) – Response Evaluable Analysis Set
14.2.6.2	Duration of Stable Disease (iRECIST) – KM – Response Evaluable Analysis Set
14.2.7	Progression Free Survival (RECIST) – KM – Response Evaluable Analysis Set
14.2.8	Progression Free Survival (iRECIST) – KM – Response Evaluable Analysis Set
14.2.9	Overall Survival – KM – Response Evaluable Analysis Set
14.3.1.1	Overall Summary of Treatment Emergent Adverse Events – Safety Analysis Set

Table Number	Table Title
14.3.1.2	Treatment Emergent Adverse Events by System Organ Class and Preferred Term – Safety Analysis Set
14.3.1.3	Treatment Emergent Adverse Events by System Organ Class, Preferred Term and Severity – Safety Analysis Set
14.3.1.4.1	Treatment Emergent Adverse Events Related to Etigilimab by System Organ Class and Preferred Term – Safety Analysis Set
14.3.1.4.2	Treatment Emergent Adverse Events Related to Nivolumab by System Organ Class and Preferred Term – Safety Analysis Set
14.3.1.4.3	Treatment Emergent Adverse Events Related to Etigilimab and Nivolumab by System Organ Class and Preferred Term – Safety Analysis Set
14.3.1.4.4	Treatment Emergent Adverse Events Related to Etigilimab or Nivolumab by System Organ Class and Preferred Term – Safety Analysis Set

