14.2.4 Response (iRECIST)

Table 14.2.2.1
Duration of Response (RECIST)
Response Evaluable Analysis Set

Duration (Days)	Cohort A EC CPI-Naive (N = XX)	Cohort C Cervical (N = XX)	Cohort E TMB-H/MSS (N = XX)	Uveal (N = XX)	Cohort F Rare Tumors (N = XX)		GCT (N = XX)	Cohort G Post-CPI (N = XX)	Cohort H Ovarian (N = XX)
					De-Diff LPS (N = XX)	UPS (N = XX)			
n	X	X	X	X	X	X	X	X	X
Mean (SD)	XX.X (XX.XX)	XX.X (XX.XX)	XX.X (XX.XX)	XX.X (XX.XX)	XX.X (XX.XX)	XX.X (XX.XX)	XX.X (XX.XX)	XX.X (XX.XX)	XX.X (XX.XX)
Median	XX.X	XX.X	XX.X	XX.X	XX.X	XX.X	XX.X	XX.X	XX.X
Q1, Q3	XX.X, XX.X	XX.X, XX.X	XX.X, XX.X	XX.X, XX.X	XX.X, XX.X	XX.X, XX.X	XX.X, XX.X	XX.X, XX.X	XX.X, XX.X
Min, Max	XX, XX	XX, XX	XX, XX	XX, XX	XX, XX	XX, XX	XX, XX	XX, XX	XX, XX
n	X	X	X	X	X	X	X	X	X
Mean (SD)	XX.X (XX.XX)	XX.X (XX.XX)	XX.X (XX.XX)	XX.X (XX.XX)	XX.X (XX.XX)	XX.X (XX.XX)	XX.X (XX.XX)	XX.X (XX.XX)	XX.X (XX.XX)
Median	XX.X	XX.X	XX.X	XX.X	XX.X	XX.X	XX.X	XX.X	XX.X
Q1, Q3	XX.X, XX.X	XX.X, XX.X	XX.X, XX.X	XX.X, XX.X	XX.X, XX.X	XX.X, XX.X	XX.X, XX.X	XX.X, XX.X	XX.X, XX.X
Min, Max	XX, XX	XX, XX	XX, XX	XX, XX	XX, XX	XX, XX	XX, XX	XX, XX	XX, XX

De-Diff LPS = Dedifferentiated Liposarcoma, UPS = Undifferentiated pleomorphic sarcoma, GCT = Germ Cell Tumors.

Note: Duration of response is the Date of first overall response of PD or date of death due to underlying cancer (whichever is first) - Date of first of the two assessments required for confirmed CR or PR. Note: No subjects were recruited into Cohort D and so this cohort is not displayed.
Note: No subjects in Cohort B are in the Response-Evaluable Analysis Set and so this cohort is not displayed here.

Source: Listing 16.2.4.1

This table shell will be used for

- 14.2.3.1 Duration of Stable Disease (RECIST v1.1)
- 14.2.5.1 Duration of Response (iRECIST)
- 14.2.6.1 Duration of Stable Disease (iRECIST)

Table 14.2.2.2
 Duration of Response (RECIST) - KM
 Response Evaluable Analysis Set

Time (days)	Cohort A EC CPI-Naïve (N = XX)			Cohort C Cervical (N = XX)			Cohort G Post-CPI (N = XX)			Cohort H Ovarian (N = XX)		
	n	N#	Kaplan-Meier Estimate	n	N#	Kaplan-Meier Estimate	n	N#	Kaplan-Meier Estimate	n	N#	Kaplan-Meier Estimate
XX	XXX	XXX	0.XXX	XXX	XXX	0.XXX	XXX	XXX	0.XXX	XXX	XXX	0.XXX
XX	XXX	XXX	0.XXX	XXX	XXX	0.XXX	XXX	XXX	0.XXX	XXX	XXX	0.XXX
XX	XXX	XXX	0.XXX	XXX	XXX	0.XXX	XXX	XXX	0.XXX	XXX	XXX	0.XXX
XX	XXX	XXX	0.XXX	XXX	XXX	0.XXX	XXX	XXX	0.XXX	XXX	XXX	0.XXX
XX	XXX	XXX	0.XXX	XXX	XXX	0.XXX	XXX	XXX	0.XXX	XXX	XXX	0.XXX

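### Descriptive duration summaries that ignore censoring are planned beside the Kaplan-Meier ones and will generally understate DoR and DoSD

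*SAP*

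**What the plan says.** SAP 10.8.2.2 (DoR): "The duration of response will be summarised by cohort using descriptive summaries, which will not account for censoring". SAP 10.8.2.3 (DoSD): "The duration of stable disease will be summarised by cohort using descriptive summaries, which will not account for censoring". SAP 10.8.3.3 and 10.8.3.4 (PFS by RECIST and by iRECIST): "Progression-free survival will be summarised by cohort, and sub-cohort for cohort F, using descriptive summaries, which will not account for censoring". SAP 10.8.3.5 (OS): "Overall Survival will be summarised by cohort, and sub-cohort for cohort F, using descriptive summaries, which will not account for censoring". SAP 10.8.3.2 repeats the DoR sentence for iRECIST.

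In each section the next sentence adds the censoring-aware analysis. For DoR it begins: "Additionally, Kaplan-Meier curves will be produced for each cohort along with a table summarising the median and 25th and 75th percentiles", and it states that these percentiles include censoring. Protocol 9.3.1 says: "Overall survival, PFS, and DoR will be summarized for each group using Kaplan-Meier methodology". That sentence does not name DoSD.

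In SAP 13.2, DoR and DoSD each have a non-KM table and a KM table. The non-KM tables are 14.2.2.1 (titled "Duration of Response (RECIST v1.1) – Response Evaluable Analysis Set"), 14.2.3.1, 14.2.5.1 and 14.2.6.1. Their common shell in Section 14 shows n, mean (SD), median, quartiles and range. Its footnotes define the duration by event dates and do not mention censoring. PFS and OS have only KM tables: 14.2.7, 14.2.8 and 14.2.9.

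**The concern.** A time censored at the last assessment is a lower bound on the duration. Counting it as complete, or dropping the subject because no event date exists, both tend to pull the mean and median down. DoR would then be reported with two medians that generally differ, and nothing in Table 14.2.2.1 would tell the reader that one of them ignores censoring. DoSD has the same problem.

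The descriptive figure is also undefined. The DoR and DoSD formulas need a progression date or a cancer-death date, and no rule says what a censored subject contributes. Two programmers could follow the SAP and produce different tables.

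These durations have a use. Protocol 1.4.1 expects ORR together with DoR to inform later studies of the combination, and no test stands between the estimates and that use.

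**Working it through.** **Plan's own figure.** There is none. The documents state no expected duration, censored fraction or bias, so every censored fraction below is an assumption.

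**Exponential case.** Let the event time T have rate λ and the independent censoring time C have rate μ.
- The observed time X = min(T, C) is exponential with rate λ + μ.
- Its median is ln 2/(λ + μ), against the true ln 2/λ. The ratio is λ/(λ + μ) = P(event) = 1 − P(censored). The mean has the same ratio.
- Here X has the same distribution whether or not it ends in an event, so keeping only subjects with events gives the same result.
- Naive mean and median are therefore 10% low at 10% censored, 30% at 30%, 50% at 50% and 60% at 60%.

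**Other patterns.** Simulation used 400,000 draws, Weibull event times (shape 0.7, 1.0 or 1.5) and independent exponential, uniform or fixed-time censoring. The table gives the percentage by which the naive figure is too low at 30% censored.

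| Shape | Censoring | Mean, censored counted as events | Mean, events only | Median, censored counted as events | Median, events only |
|---|---|---|---|---|---|
| 0.7 | exponential | 42 | 50 | 32 | 45 |
| 0.7 | uniform | 44 | 57 | 26 | 46 |
| 0.7 | fixed | 46 | 68 | 0 | 49 |
| 1.0 | exponential | 30 | 30 | 30 | 30 |
| 1.0 | uniform | 30 | 37 | 26 | 32 |
| 1.0 | fixed | 30 | 52 | 0 | 38 |
| 1.5 | exponential | 23 | 16 | 26 | 17 |
| 1.5 | uniform | 22 | 20 | 23 | 19 |
| 1.5 | fixed | 18 | 36 | 0 | 27 |

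The mean is low by 16% to 68% and the median by 0% to 49%.

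**Checking the two ends for the median by hand.** With a fixed cut-off c and 30% censored, c is the 70th percentile of T.
- Censored times counted as events: c lies above the median, so the median of min(T, c) equals the median of T. The bias is 0%.
- Events only: the median among events is the 35th percentile of T. With Weibull shape k, its ratio to the true median is [ln(1/0.65)/ln 2]^(1/k) = (0.4308/0.6931)^(1/k) = 0.6215^(1/k). For k = 1 this is 0.62 (38% low). For k = 0.7 it is 0.51 (49% low).

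**KM on the same data.** The KM median was within 0.1% of the truth in every scenario where it was reached. With a fixed cut-off and 60% censored it was not reached, and KM reports that. The naive median still printed a value there: 18% to 35% low with censored times counted as events, and 53% to 80% low with events only. The KM result relies on censoring being independent of the event time, as simulated.

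**The case against.** The strongest reply is that the sound analysis is already planned. Every endpoint gets KM curves and KM percentiles, and the SAP text says openly that the descriptive figures ignore censoring. No hypothesis test is planned (SAP 10.1.3), DoR and DoSD are secondary, PFS and OS are exploratory, and the primary endpoint, ORR, is untouched. All of this stands and limits the point to an avoidable flaw in supporting tables. It does not justify printing them, because the warning is in the SAP text and not in the shell.

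A reader might also infer several stronger things that the documents do not support:
- **That the protocol allows KM only.** The opening of Protocol Section 9 provides for means and medians of continuous variables. Section 9.3 calls for summary statistics on all endpoints and allows the SAP to add analyses. SAP Section 11 does not list the descriptive summaries as a change, but they do not breach the protocol.
- **That PFS and OS will also show two medians.** The table list gives them only KM tables. The defect there is that text and table list disagree.
- **That the uncorrected table is the more prominent one.** Only the KM results have figures, and neither shell carries a confidence interval.
- **That the bias is about the censored fraction in general.** That rule needs exponential events and exponential censoring. With one fixed cut-off, up to 50% censored and censored times counted as events, the naive median has no bias.
- **That censoring will be heavy.** SAP 6.3 says the study was terminated, which makes some censoring of ongoing subjects likely, but no fraction is given. The Phase 1 study in Protocol 1.2, in a different population, had PFS of 10% and 25% at 6 months and 0% at 12 months, which suggests little censoring for PFS.

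**Conclusion.** The point holds for DoR and DoSD, under RECIST v1.1 and iRECIST. Four planned tables will show means, medians and quartiles that ignore censoring, follow no stated rule for censored subjects, and sit beside KM figures with which they will generally disagree. The direction of bias is generally downward. Its size cannot be fixed from the documents. At an assumed 30% censored, the median is low by 0% to 49% and the mean by 16% to 68%, depending on hazard shape, censoring pattern and handling, with 30% for both in the fully exponential case. For PFS and OS the finding is a mismatch between SAP text and table list. It should be corrected before reporting, but it does not affect the primary analysis.

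**What to change.** 1. In SAP 10.8.2.2, 10.8.2.3 and 10.8.3.2 to 10.8.3.5, delete the sentences on descriptive summaries that do not account for censoring. This also brings the PFS and OS text into line with the table list.
2. Remove Tables 14.2.2.1, 14.2.3.1, 14.2.5.1 and 14.2.6.1 and their shell.
3. In the KM shell (Table 14.2.2.2 and the tables that reuse it), keep the median and quartiles. Add a 95% CI for the median and the numbers of subjects with an event and censored. The shell already gives cumulative events and numbers at risk, but no censored count and no interval.
4. Keep individual times in Listings 16.2.6.4.1 and 16.2.6.4.2 and add a censoring flag, which those shells lack.

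The cost is SAP wording, four fewer tables, a few extra lines in the KM shell and one flag per duration in two listings. No new data are needed.
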